Efficacy Endpoints: The primary efficacy endpoint is COVID-19-related hospitalization or all-cause death through Day 29. This endpoint evaluates clinically relevant measures for mild and moderate COVID-19 over a relevant duration of time. Development of severe or critical COVID-19, a key secondary endpoint, will be evaluated using pre-specified disease severity definitions and will provide a systematic estimate of disease progression from mild or moderate COVID-19 (required for study entry) to a worse severity. A secondary endpoint is the time to sustained resolution of COVID-19 symptoms through Day 29. Although recovery from COVID-19 is variable, Day 29 is an appropriate time period for assessment of resolution of COVID-19 based on published findings suggesting that resolution of mild infection occurs over a period of approximately 2 to 3 weeks (WHO 2020). Data from SARS-CoV-2 mAb trials enrolling a similar population further support the Day 29 assessment period, with the majority of patients experiencing symptom resolution in <14 days (Celltrion Healthcare Hungary 2021; Eli Lilly and Company 2022a; GlaxoSmithKline 2022; Regeneron 2022).

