3.5.1. Clinical Efficacy Endpoints

COVID-19-related hospitalization or all-cause death through Day 29 (primary endpoint):

COVID-19-related hospitalizations include visits for attention to worsening signs or symptoms attributed to COVID-19, in the opinion of the investigator.

- **Hospitalization** is defined as ≥ 24 hours of acute care in a hospital or acute care facility (includes emergency rooms, intensive care units, acute care facilities created for COVID-19 pandemic hospitalization needs, or other acute care facilities).
- **Through Day 29** is defined as the admission date for the hospitalization or acute care facility occurring from Day 1 (postdose) up to and including Day 29.
- **All-cause death** is defined as death for any reason from Day 1 (postdose) through Day 29.

Severe/critical COVID-19 or all-cause death through Day 29: All-cause death is defined as death for any reason from Day 1 (postdose) through Day 29. Severity is based on the investigator's assessment of severity (eCRF COVID-19 Severity Assessment) per the following protocol definitions:

- **Severe COVID-19** is defined as having a positive test by standard RT-PCR assay or equivalent test plus the following:
 - Symptoms suggestive of severe systemic illness with COVID-19, which could include any symptom of moderate illness or shortness of breath at rest, or respiratory distress including the need for initiation of oxygen therapy.
 - Clinical signs suggestive of severe systemic illness with COVID-19, such as respiratory rate ≥ 30 breaths per minute, heart rate ≥ 125 beats per minute, $\text{SpO}_2 \leq 93\%$ on room air at sea level or ratio of arterial oxygen partial pressure to fractional inspired oxygen ($\text{PaO}_2/\text{FiO}_2$) < 300 mm Hg.
 - No criteria for critical severity.
- **Critical COVID-19** is defined as having a positive test by standard RT-PCR assay or equivalent test plus evidence of critical illness, defined by at least one of the following:
 - Respiratory failure based on resource utilization requiring at least one of the following:

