 - Endotracheal intubation and mechanical ventilation, oxygen delivered by high-flow nasal cannula (heated, humidified, oxygen delivered via reinforced nasal cannula at flow rates > 20 L/min with fraction of delivered oxygen ≥ 0.5), noninvasive positive pressure ventilation, extracorporeal membrane oxygenation, or clinical diagnosis of respiratory failure (ie, clinical need for one of the preceding therapies, but the preceding therapies cannot be administered in setting of resource limitations).

- Shock (defined by systolic blood pressure <90 mmHg, diastolic blood pressure <60 mmHg, or requiring vasopressors). **Note:** Shock is per investigator diagnosis/assessment.
- Multiorgan dysfunction/failure.

Note: A clinical diagnosis of respiratory failure (in the setting of resource limitation) in which the management deviates from standard of care should be recorded as part of formal data collection.

Regardless of investigator's assessment of severity, severe/critical COVID-19 will be imputed for participants who met the primary efficacy endpoint definition in the analysis.

COVID-19-related emergency room visits, COVID-19-related hospitalization, or all-cause death through Day 29: Defined as any stay in a hospital or acute care facility regardless of duration (includes emergency rooms, intensive care units, acute care facilities created for COVID-19 pandemic hospitalization needs, or other acute care facilities) for attention to worsening signs or symptoms attributed to COVID-19 in the opinion of the investigator or all-cause death through Day 29.

COVID-19-related medically attended visits or all-cause death through Day 29: Defined as for the primary efficacy endpoint, but also includes any medically attended visits, in-person, or telemedicine, not specified in the protocol. These include unscheduled in-person or telemedicine visits conducted by the investigator for the purpose of evaluating worsening signs or symptoms attributed to COVID-19 or emergency room, urgent care center or physician office visits, or hospitalization for attention to worsening signs or symptoms attributed to COVID-19, in the opinion of the investigator.

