5.5.3. Key Secondary Endpoints and Analyses

[Appendix H](#) provides an overview of the main estimation and sensitivity analyses for the key secondary estimands (Estimand 2 and Estimand 3).

To control the overall type I error rate at .05 (2-sided), a hierarchical testing procedure will be used, such that testing for the key secondary analyses difference will proceed only if the treatment difference is statistically significant in the primary analysis.

The key secondary endpoints will be tested in the following order:

1. Severe/critical COVID-19 or all-cause death through Day 29
2. COVID-19-related emergency room visit, COVID-19-related hospitalization, or all-cause death through Day 29
3. Time to sustained resolution of COVID-19 symptoms through Day 29

For binary endpoints, the analysis will use the same methodology as the primary efficacy endpoint for determining a standardized estimator for a binary outcome (standardized risk difference/standardized relative risk reduction) with adjustment for the following prognostic factors: age (continuous), sex (categorical), baseline serostatus (categorical as positive; negative), BMI (continuous) and baseline viral load (continuous as \log_{10} copies/mL) and will be conducted on the mFAS-non-Omicron analysis set. Similar to the primary analysis, the standard error of the standardized estimator will be estimated using the delta method.

For the first key secondary endpoint, if the determination of investigator assessment of COVID-19 severity is missing at a visit, it will be imputed as not severe/critical COVID-19 (or all-cause death) unless the participant is hospitalized due to COVID-19 at the time of the visit. In this case, the assessment of COVID-19 severity will be imputed as severe/critical COVID-19.

For the second key secondary endpoint, missing data will be imputed as not having a COVID-19-related emergency room visit, COVID-19-related hospitalization, or all-cause death through Day 29. The number and percentages of participants who experience the event and do not experience the event will be summarized by treatment group, including summaries of missing data, and each component of the endpoint. The observed risk difference (placebo minus ADG20) with 95% CI (using the Miettinen-Nurminen method), observed relative risk reduction, standardized risk difference between the ADG20 arm and placebo arm with 95% CI and associated p-values, and standardized relative risk reduction with 95% CI will be provided.

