7. CHANGES IN THE PLANNED ANALYSIS

There are no changes to the analyses presented in the protocol.

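### Key secondary 1 contains the primary endpoint by construction, so its significance alone does not show an effect on severity as the protocol defines it

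*SAP*

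**What the plan says.** Protocol 1.3.2 presents progression to severe or critical disease as a key secondary endpoint that "will be evaluated using pre-specified disease severity definitions and will provide a systematic estimate of disease progression from mild or moderate COVID-19". Protocol 2.2.2 defines severe and critical disease by symptoms, vital signs, oxygenation, respiratory support, shock and organ failure. Admission to hospital is on neither list.

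SAP 3.5.1 starts from the same place: "Severity is based on the investigator's assessment of severity (eCRF COVID-19 Severity Assessment) per the following protocol definitions". After the definitions it adds that, whatever grade the investigator gave, "severe/critical COVID-19 will be imputed for participants who met the primary efficacy endpoint definition in the analysis".

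The hospitalization part of the primary endpoint means at least 24 "hours of acute care in a hospital or acute care facility (includes emergency rooms, intensive care units" and similar places), for worsening COVID-19 in the investigator's opinion. It carries no severity criterion.

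SAP 5.5.3 has a separate, narrower rule. A missing visit grade counts as not severe/critical unless the participant is in hospital for COVID-19 at that visit: "In this case, the assessment of COVID-19 severity will be imputed as severe/critical COVID-19". The planned sensitivity analyses in SAP 5.5.3.1 are multiple imputation under MAR and a repeat in the per-protocol set. SAP 7 states: "There are no changes to the analyses presented in the protocol".

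**The concern.** The rule replaces grades that were recorded, not only grades that are missing. A participant kept for 24 hours, discharged alive and graded moderate throughout is analysed as severe/critical.

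Key secondary 1 is the first test after the primary in the alpha-controlled sequence. A significant result would naturally be reported as prevention of severe or critical disease. If much of it comes from admissions that were never graded severe, that wording goes beyond what was measured.

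The planned outputs would not reveal this. Both sensitivity analyses keep the rule. The programmatic severity derivation (SAP 5.2.2, Table 3) also counts a COVID-19-related stay of at least 24 hours as severe, so it is no independent check. The summary of endpoint components in SAP 5.5.3 is described for the second key secondary endpoint.

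**Working it through.** **1. The plan's own figure.** SAP 4.2 gives about 320 participants (160 per arm at 1:1), 12% placebo, 70% relative reduction (0.12 × 0.30 = 3.6% on ADG20) and 2-sided alpha 0.05.

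Power = Φ{[|p0 − p1| − 1.96·√(2p̄(1 − p̄)/n)] / √(p0(1 − p0)/n + p1(1 − p1)/n)}

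With p̄ = 0.078, the pooled SE is √(2 × 0.078 × 0.922/160) = 0.0300 and the unpooled SE is √((0.1056 + 0.0347)/160) = 0.0296. Power = Φ[(0.084 − 0.0588)/0.0296] = Φ(0.85) = 0.803, which matches the stated 80% or so. The documents give no rate or power for key secondary 1.

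**2. What the rule adds.** Deaths count in both endpoints with or without the rule. It therefore adds only survivors with a COVID-19-related stay who were not graded severe or critical. Key secondary 1 = primary events + participants graded severe/critical without a qualifying stay.

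**3. A count example.** Expected primary events are 160 × 0.12 ≈ 19 and 160 × 0.036 ≈ 6. Suppose 6 in each arm were graded severe/critical or died, and nobody was severe outside hospital.
- With the rule: 19 vs 6. p̄ = 25/320 = 0.0781, SE = √(0.0781 × 0.9219 × 2/160) = 0.0300, z = (13/160)/0.0300 = 2.71, p = 0.007.
- On recorded grades: 6 vs 6, p = 1.0.

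This needs 0.084/0.12 = 70% of placebo primary events, and none on ADG20, to be non-severe.

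**4. Simulation.** 400,000 trials per setting, 160 per arm, primary rates 12% vs 3.6%, unadjusted pooled z-tests. The covariate-adjusted estimator was not simulated. Two inputs are assumptions because the documents give neither: the share of primary events that are graded severe/critical or fatal, and the rate of severe disease outside hospital. Simulated primary power is 0.82, slightly above the formula value.

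*Case A: graded severity or death equal in both arms (3.6% among primary events, plus the outside-hospital rate).*

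| Severe outside hospital, each arm | Key secondary 1 significant | Same, given a significant primary | Recorded grades or death |
|---|---|---|---|
| 0% | 0.822 | 1.000 | 0.047 |
| 1% | 0.775 | 0.915 | 0.049 |
| 2% | 0.733 | 0.859 | 0.048 |
| 3% | 0.695 | 0.810 | 0.048 |
| 5% | 0.622 | 0.722 | 0.050 |

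With 1% instead of 3.6% severe among primary events and none outside hospital, the recorded-grade figure is 0.032, and key secondary 1 stays at 0.822.

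*Case B: same severe share h of primary events in both arms, 1% severe outside hospital.* With the rule the rates are 13.0% vs 4.6%. Without it they are 0.12h + 0.01 vs 0.036h + 0.01.

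| h | Rates without the rule | Power without | Power with |
|---|---|---|---|
| 30% | 4.6% vs 2.1% | 0.23 | 0.775 |
| 50% | 7.0% vs 2.8% | 0.42 | 0.775 |
| 70% | 9.4% vs 3.5% | 0.58 | 0.775 |
| 90% | 11.8% vs 4.2% | 0.72 | 0.775 |
| 100% | 13.0% vs 4.6% | 0.775 | 0.775 |

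In Case B there is a real effect on graded severity. The gap shows how much of the apparent strength of evidence on severity is borrowed from admissions.

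**The case against.** The strongest counter-argument is that the rule catches real severe disease that grading misses. Grades are assigned per visit (protocol 6.3.2.2), on Days 3, 5, 7, 11, 14, 21 and 29, and the documents do not say that a grade covers the interval since the last visit. Someone admitted on Day 8, given oxygen, discharged on Day 10 and graded moderate on Day 11 has no missing grade and was not in hospital at a visit, so the SAP 5.5.3 rule never applies. Yet starting oxygen belongs to the severe definition. The timing is realistic: the protocol cites admission at a median of 7 (section 1.2) or 8 (section 1.3.2) days from onset and enrols within 5 days of onset. This stands, and it is why dropping the rule from the tested endpoint is not recommended.

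Other points have partial force.
- Counting a stay of at least 24 hours as severe agrees with SAP Table 3. But neither follows from protocol 2.2.2.
- Protocol 7.4 leaves imputation details to the SAP, and SAP 1 allows non-principal additions. Whether SAP 7 had to list the rule is therefore arguable. But replacing a recorded value changes what is counted, which goes beyond filling a gap.
- Key secondary 2 also contains every primary event. True, but its name says so.
- SAP 5.5.5 tabulates hospital and ICU stays. That helps, but it does not separate graded events from those added by the rule.
- Case A is extreme, and at a 90% severe share the rule changes little (0.72 to 0.775). Both stand.

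**Conclusion.** The point holds as a matter of definition and labelling. Key secondary 1 includes the primary endpoint by construction, and no planned analysis shows whether graded severity differed between arms. The primary test is unaffected.

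The size rests on assumed inputs. If graded severity or death is equal in both arms, key secondary 1 is significant in about 62% to 82% of trials with 0% to 5% severe outside hospital, against 3% to 5% on recorded grades. With a common severe share, the rule moves power from between 0.23 (30% share) and 0.72 (90% share) to about 0.775.

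A reader might infer more than the documents support:
- *That key secondary 1 can say nothing about severity.* Deaths and participants graded severe outside hospital count either way, and if most admissions are graded severe it is informative.
- *That type I error is inflated.* The rule is pre-specified and applies to both arms, so error is controlled for the composite as defined.
- *That eCRF grades are altered.* The SAP imputes the value in the analysis only.
- *That the SAP 5.5.3 rule becomes redundant.* It works per visit and also sets missing grades outside hospital to not severe.

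**What to change.** Keep the composite in the hierarchy, with four changes to the SAP before unblinding.
1. Label it *COVID-19-related hospitalization, investigator-assessed severe/critical COVID-19, or all-cause death*.
2. List it in SAP 7 as a change from the protocol, reconciling SAP 3.5.1 and 5.5.3 with protocol 1.3.2 and 2.2.2.
3. Add a named supportive analysis of investigator-assessed severe/critical COVID-19 or all-cause death without the rule, keeping the missing-grade rule of SAP 5.5.3.
4. Tabulate events by arm and source: graded severe/critical, counted only through the rule, and death.

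Base any statement about severity on items 3 and 4 read together, because the supportive analysis can miss severe disease between visits.

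The cost is one extra analysis, one table and a narrower label for the alpha-controlled claim. The tested endpoint does not change, so no power is lost in the hierarchy. The supportive analysis will have less power (0.23 to 0.72 in Case B for shares of 30% to 90%), so a non-significant result there would not show absence of an effect on severity.

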4.2. Discontinuation of Study Drug or Withdrawal from the Study

4.2.1. Premature Discontinuation from Study Drug

In rare instances, it may be necessary for a participant to permanently discontinue study drug. Premature discontinuation does not require or represent discontinuation from the study.

In the event of study drug discontinuation for safety reasons or participant refusal, the participant should remain in the study until all protocol-specified procedures and assessments are completed through the EOS Visit at Month 14. If a participant was randomized but did not receive study drug, these assessments are not required; however, the participant must be followed for efficacy endpoints through Day 29, unless the participant has withdrawn from the study. The estimated dose of study drug received prior to discontinuation will be documented.

Reasons for premature discontinuation from study drug administration must be recorded in the eCRF and may include, but are not limited to, the following:

- Occurrence of an AE that, in the opinion of the investigator, warrants the participant's permanent discontinuation from study drug administration.
- Participant refusal to continue study drug administration.

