7.4. Statistical Analyses

Statistical analysis will be performed using SAS software Version 9.4 or later. Continuous variables will be summarized using the mean, standard deviation, median, first and the third quartiles, minimum value, and maximum value. Categorical variables will be summarized using frequency counts and percentages. Data will be listed.

The objectives and endpoints for all study phases are shown in [Table 2-1](#).

Unless otherwise specified, estimations involving the primary and secondary endpoints will follow a treatment policy strategy for the handling of intercurrent events, which uses and analyzes all data for the endpoints after the intercurrent event has occurred. When a hypothetical strategy is used, data may be censored in the case of a time to event endpoint or imputed in the case of continuous or binary endpoints.

Estimand attributes, intercurrent events of interest, and rationales for intercurrent event handling strategies for the primary and key secondary estimands will be fully described in the SAP. The main estimation for the primary efficacy and key secondary efficacy endpoints is described in [Section 7.6](#) and [Section 7.7](#). Definitions of censoring and details of imputation methodology will be provided in the SAP.

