7.7. Main Estimation Utilizing Key Secondary Efficacy Endpoints

The key secondary endpoints will be tested in the following order in the mFAS-non-Omicron analysis set:

1. Severe/critical COVID-19 or all-cause death through Day 29
2. COVID-19-related emergency room visit, COVID-19-related hospitalization, or all-cause death through Day 29.
3. Time to sustained resolution of COVID-19 symptoms through Day 29

Treatment differences in the proportion of participants with severe/critical COVID-19 or all-cause death through Day 29 will be presented with 95% CIs and tested using the analysis procedure outlined for the primary efficacy outcome.

Treatment differences in proportion of participants with COVID-19-related emergency room visits, COVID-19-related hospitalizations or all-cause death through Day 29 will be presented with 95% CIs and tested using the analysis procedure outlined for the primary outcome.

Time to sustained resolution in COVID-19 symptoms through Day 29 will be analyzed by KM methodology and stratified Cox Proportional Hazard model. Survival curves between ADG20 and placebo will be compared using a log-rank test stratified by age (categorical as 12-17, 18-65, and >65 years). A stratified Cox Proportional Hazard model will be used to estimate the hazard ratio where the model includes age (categorical as 12-17, 18-65, and >65 years) as stratification variable and sex (categorical), baseline serostatus (categorical), baseline BMI (continuous), and baseline viral load (continuous as \log_{10} copies/mL) as covariates. Comparison of the survival distributions will use the score test for the hazard ratio from the Cox model. Estimand attributes for the key secondary objective and supportive estimands will be fully described in the SAP.

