Time to sustained recovery (improvement or resolution) of COVID-19 symptoms through Day 29: Defined as the time from the first dose date to the earliest date when sustained improvement or sustained resolution of COVID-19 symptoms is met (as detailed below) through Day 29. COVID-19 symptoms assessed include fever, chills, cough, sore throat, congestion, shortness of breath/difficulty breathing at rest, shortness of breath/difficulty breathing with exertion, muscle or body aches, fatigue, headache, nausea, vomiting, and diarrhea. Loss of taste/smell is excluded from this analysis.

Time to sustained improvement of COVID-19 symptoms through Day 29: Defined as the time from the first dose date to the first date when all of the above symptoms are scored as moderate or severe at baseline are scored as mild or absent, all of the above symptoms scored as mild or absent at baseline are scored as absent, and with no symptom worsening or new symptoms, except for cough, fatigue, and headache which may be mild or absent, through Day 29.

Time to sustained resolution of COVID-19 symptoms through Day 29: Defined as time from the first dose date to the first date when all of the above symptoms are scored as absent with no symptom recurrence or new symptoms, except cough, fatigue, and headache which may be mild or absent, through Day 29.

Censoring rules for time to COVID-19 symptoms through Day 29 analysis:

- Participants who are randomized but not treated are censored at Day 1.

- Participants who have any COVID-19-related hospitalization (≥ 24 hours) or all-cause death through Day 29 (as defined in the primary endpoint) will be censored at Day 30.
- Participants who have not been followed through Day 29 visit (discontinuation from study or incomplete follow-up at the time of analysis) will be censored at the last contact date.
- Participants who have completed the Day 29 visit and do not experience a defined event through Day 29 will be censored at Day 30.

[Table 2](#) provides further programming details.

Table 2: Criteria for Sustained Improvement and Sustained Resolution of COVID-19 Symptoms Through Day 29

COVID-19 Symptoms	Baseline Severity	Criteria for Sustained Improvement	Criteria for Sustained Resolution

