4. GENERAL STATISTICAL CONSIDERATIONS

4.1. General Rules and Considerations

Continuous variables will be summarized using the following descriptive summary statistics: the number of participants (n), mean, SD, median, first and third quartiles, minimum (min), and maximum (max).

Categorical variables will be summarized using frequency counts and percentages.

Baseline value, unless specified otherwise, is defined as the last non-missing measurement (scheduled or unscheduled) collected on or before the dose of study drug. If the date of dosing is missing, the date of randomization will be used instead.

Unless otherwise specified, the display precision for the summary statistics of all numerical variables will follow programming standards. Please see [Appendix A](#) for variable display standards.

When count data are presented, the percentage will be suppressed when the count is zero in order to draw attention to the non-zero counts. A row denoted “Missing” will be included in count tabulations as needed to account for dropouts and missing values. The denominator for all percentages will be the number of participants in the treatment group within the analysis set of interest, unless otherwise specified.

Change from baseline is defined as the value at the post-baseline visit minus the value at the baseline visit.

Study Day 1 is the calendar day that study drug is administered. Subsequent study days are calculated as the date of assessment/event – date of injection + 1. If a participant is not dosed, the date of randomization is used to define Study Day rather than the date of injection.

Time-to-event variables are defined from the date of dosing. If a participant is not dosed, the date of randomization is used.

All summaries involving diary data will be based on distinct diary date entries.

Unscheduled visits: Unscheduled visit measurements will be included in the analysis as follows:

- In scheduled visit windows per specified visit windowing rules.
- In the derivation of baseline measurements.
- In the derivation of maximum/minimum change from baseline values and worst post-baseline values for safety analyses.
- In individual participant data listings as appropriate.

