4.5.3. SARS-CoV-2 Variant Specific Analysis Sets

WGS will be used to determine a participant's SARS-CoV-2 infecting variant (Delta, Omicron, and others) based on the NP or saliva sample collected at baseline; if the baseline sample is missing, the available post-baseline NP or saliva sample will be used. Any participants with a missing WGS result will be classified as suspected non-Omicron or Omicron variant by comparing their randomization date with the date of the first WGS-confirmed Omicron participant enrolled from the same country. If there is no WGS-confirmed Omicron participant enrolled from the same country in the study, the date of emergence of Omicron in the country, based on publicly available epidemiology data will be used (see [Appendix E](#)). A final clinical and virological review (with adjudication as needed) may be performed.

Modified Full Analysis Set with Non-Omicron SARS-CoV-2 Variant (mFAS-non-Omicron): will include all randomized participants with COVID-19 due to WGS-confirmed or suspected non-Omicron SARS-CoV-2 variants, regardless of whether the participant received study drug. The mFAS-non-Omicron is the primary efficacy population.

Modified Full Analysis Set with Omicron SARS-CoV-2 Variant (mFAS-Omicron): will include all randomized participants with COVID-19 due to WGS-confirmed or suspected Omicron SARS-CoV-2 variant, regardless of whether the participant received study drug.

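### Censoring every untreated participant at Day 1 makes the third key secondary endpoint in effect a treated-only analysis, although its analysis set keeps these participants

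*SAP*

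**What the plan says.** SAP 3.5.1 lists four censoring rules for the symptom analyses. The first reads: "Participants who are randomized but not treated are censored at Day 1". The second censors anyone with a COVID-19-related hospitalization or a death through Day 29 at Day 30. The third uses last contact for incomplete follow-up. The fourth uses Day 30 for those who complete Day 29 without the event. No order of precedence is given.

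Four other provisions bear on undosed participants:

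- **Analysis set.** Protocol 7.7 says: "The key secondary endpoints will be tested in the following order in the mFAS-non-Omicron analysis set". SAP 4.5.3 defines that set as randomized participants with confirmed or suspected "non-Omicron SARS-CoV-2 variants, regardless of whether the participant received study drug".
- **Follow-up.** Protocol 4.2.1 first relaxes the procedures ("If a participant was randomized but did not receive study drug, these assessments are not required") and then adds that "the participant must be followed for efficacy endpoints through Day 29, unless the participant has withdrawn from the study".
- **Time origin.** SAP 4.1: "Time-to-event variables are defined from the date of dosing. If a participant is not dosed, the date of randomization is used".
- **Missing diaries.** SAP Appendix F, rule e, excludes a participant from these analyses only if all data are missing for all symptoms.

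**The concern.** The set is defined by randomization, the undosed have a defined time zero, and the protocol asks for their efficacy outcomes. The first censoring rule then removes them from the comparison at the outset, with no reason given. Where the SAP wants a dosing requirement it writes one: mFAS-PCR (SAP 4.5.4) requires receipt of study drug, and the Per-Protocol Set (SAP 4.5.5) requires the full dose. Its absence from mFAS-non-Omicron therefore reads as deliberate.

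At stake is the meaning of the last test in the multiplicity-controlled hierarchy: it would be reported as an all-randomized comparison while estimating a treated-only one. SAP 5.5.3.1 repeats the key secondary analyses in the Per-Protocol Set, and the Day 1 rule removes part of the contrast which that repeat should show. There is also a programming ambiguity. For an untreated participant who is hospitalized for COVID-19 or dies, Day 1 means never at risk, whereas Day 30 means at risk throughout and never resolved.

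**Working it through.** **1. The plan's own figures.** Neither document states a sample size, power, event count or effect assumption for the symptom endpoint, so there is nothing to reproduce for it. The figures in SAP 4.2 concern the primary endpoint, and they do reproduce. For 5% versus 1.5%, 90% power and two-sided 0.05, the pooled normal formula gives 538 per arm, or 1076 in total against the stated 1084. With 160 per arm and 12% versus 3.6%, power is 80.3% against about 80%. Only the population size, about 320, is used below.

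**2. What Day 1 censoring does.** The Cox partial likelihood and the log-rank test use, at each event time t, the participants still under observation at t. A participant censored at Day 1 is in none of these risk sets if the first event falls after Day 1, and so contributes nothing. This was checked by simulation: 160 per arm, 400 runs, exponential times with an assumed placebo median of 14 days, follow-up to Day 29, unstratified and unadjusted Cox model. In every run the estimate with untreated participants censored at Day 1 equalled the estimate with them deleted; the largest difference in log hazard ratio was about 2e-15.

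**3. How many people.** The number untreated is not in the documents. Assumed shares of 320 give:

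- 1%: 320 × 0.01 = 3.2
- 3%: 320 × 0.03 = 9.6
- 5%: 320 × 0.05 = 16

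**4. Effect on the hazard ratio.** Same simulation, with an assumed true hazard ratio of 1.4 in treated participants (above 1 means faster resolution on ADG20). Untreated participants in either arm resolve at the placebo rate times the factor shown. Followed means that their outcome is observed through Day 29.

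| Untreated, placebo / ADG20 | Rate factor | HR, followed | HR, Day 1 rule | Mean events, followed / Day 1 rule |
|---|---|---|---|---|
| 1% / 1% | 1 | 1.415 | 1.421 | 257.3 / 254.9 |
| 3% / 3% | 1 | 1.404 | 1.422 | 256.9 / 249.8 |
| 5% / 5% | 1 | 1.394 | 1.422 | 256.6 / 244.5 |
| 5% / 0% | 0.3 | 1.497 | 1.421 | 254.2 / 251.5 |
| 5% / 0% | 2.0 | 1.376 | 1.421 | 259.0 / 251.5 |

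Compare within rows. All rows share one random seed and a small common offset: with a true hazard ratio of 1.0, the Day 1 rule averages 1.013 to 1.014.

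**5. The two dates.** The second rule covers hospitalization or death as defined for the primary endpoint, and SAP 3.5.1 counts those events from Day 1, postdose. Read by intent, the rule reaches an undosed participant and gives Day 30 while the first rule gives Day 1. Read literally, an undosed participant has no postdose period and only the first rule applies. The text does not settle which.

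**The case against.** The strongest reply is that there may be little to analyze. Protocol 4.2.1 waives the protocol-specified assessments for undosed participants, the daily diary is one of those in the Schedule of Assessments, and the duty to follow efficacy endpoints does not say whether it includes 29 days of diaries. This stands as a caveat: diary data may be sparse. It supports last-contact censoring or the Appendix F rules where data are missing. It does not support discarding data that were collected.

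It also stands that simply deleting the first rule would be a poor repair. The Day 1 diary is completed under observation before dosing (Protocol 6.2), so an undosed participant may have that entry and nothing later. Appendix F rule e would not exclude such a person, who would then sit at risk as unresolved until last contact or Day 30 with no symptom data.

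A third reply is that the SAP prevails over the protocol on methods (SAP 1) and that Protocol 7.4 leaves censoring definitions to the SAP. Both are true, but neither resolves a tension within the SAP, between 3.5.1 on one side and 4.1 and 4.5.3 on the other.

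A reader might infer more than the documents support:

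- *That the rule breaches the treatment policy strategy.* Protocol 7.4 describes that strategy as one that "uses and analyzes all data for the endpoints after the intercurrent event has occurred", but only unless otherwise specified. Non-treatment is not among the intercurrent events in SAP Appendix G, and Appendix H sets out no estimand for the symptom endpoint.
- *That it contradicts SAP 4.1 outright.* A time origin at randomization is compatible with censoring on Day 1; the rule merely leaves that origin without use here.
- *That all efficacy follow-up of the untreated is lost.* The rule is confined to the symptom time-to-event analyses.
- *That two rules certainly give one person two dates.* The postdose wording makes this likely, not certain.

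**Conclusion.** The point holds, as a minor one. As written, the rule makes time to sustained resolution (key secondary 3) in effect a treated-only analysis within a set that keeps the untreated. It does the same to sustained recovery (secondary) and sustained improvement (exploratory). The exact equivalence assumes that no event falls on Day 1. The rule does not alter the primary endpoint or the two binary key secondary endpoints.

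The size is probably small and cannot be fixed from the documents. With 1% to 5% untreated, balanced between arms, the hazard ratio moves from 1.415 to 1.421 at the low end and from 1.394 to 1.422 at the high end. The larger shifts, to 1.421 from 1.497 or from 1.376, need 5% untreated in the placebo arm and none in the ADG20 arm. Nothing in the documents suggests such an imbalance in a blinded, single-dose trial; these rows show only that the direction is not predictable. A claim of material bias is therefore not supported. The median, the hazard ratio and the shares untreated are all assumptions.

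**What to change.** Replace the first censoring rule in SAP 3.5.1 before the SAP is signed and the data are unblinded (SAP 3.2), to this effect:

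1. Untreated participants are timed from randomization, as in SAP 4.1, and analyzed with their observed diary data under the same event, hospitalization/death, last-contact and Day 30 rules as everyone else.
2. The hospitalization/death rule takes precedence over the other censoring rules. For untreated participants its window runs from randomization.
3. Day 1 censoring is limited to untreated participants who have no diary data after Day 1 and no COVID-19-related hospitalization or death through Day 29.
4. The present rule, Day 1 for all untreated participants, is kept as a sensitivity analysis.

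The SAP should also say whether the efficacy follow-up in Protocol 4.2.1 includes the daily diary, and report the number untreated by arm next to the symptom results.

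The cost is a few lines of text, slightly more programming and one extra sensitivity table. The remaining weakness is that diary data in these participants may be sparse.
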